- Review of the safety data for the first patient in a cohort (Sentinel patient) must be completed on or after Day 7 before the remaining 2 patients (non-Sentinel) in that cohort may be dosed (these 2 patients may be dosed concurrently). Observation of DLT(s) in a Sentinel patient will not necessarily preclude enrollment of subsequent

patients at the same dose level; rather, DLTs occurring in Sentinel patients will be reviewed individually by the SRC (consisting of the Sponsor Medical Monitor, the CRO Medical Monitor, all active Investigators, and other study personnel as needed) to determine appropriate dosing for subsequent patients.

- After all patients in a cohort have been assessed for DLTs (i.e., after each patient either experiences a DLT or completes the end of Cycle 1 safety assessment, whichever occurs first), the SRC will review all available safety data from the cohort and determine whether to escalate to the next higher SYNB1891 dose, enroll additional patients at the current dose, de-escalate to the next lower dose, or declare that the study objectives or stopping rules have been met. The decision will be informed by the mTPI algorithm recommendation to achieve the targeted toxicity interval.
- Patients must either experience a DLT during Cycle 1 or receive at least 2 of the 3 planned SYNB1891 injections to be considered evaluable for DLT evaluations and contribute to dose-escalation decisions for a given cohort. Patients who withdraw from the study for any reason other than DLTs prior to receiving the second injection of SYNB1891 in Cycle 1 may be replaced.

Once the RP2D of Arm 2 is determined, up to 20 additional patients may be enrolled in the RP2D cohort to fully characterize the safety profile of SYNB1891 in combination with atezolizumab.

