8.2.1. Patient Replacement

Patients who terminate participation in the study for any reason other than DLTs prior to receiving the second injection of SYNB1891 in Cycle 1 will be considered ineligible for the safety assessment required for dose-escalation decisions and may be replaced.

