The protocol for Study SYNB1891-CP-001 describes the general approach to analysis of data from the study. This analysis plan describes additional detail needed to complete such an analysis. Appendix 5 provides the table of contents for summary tables, listings and figures based on this analysis plan.

B. Protocol and Amendment History

This Statistical Analysis Plan (SAP) is based on version 4.0 of Protocol Amendment SYNB1891-CP-001.

Version	Approval Date	Salient Changes, if any*
Protocol version 4.0	27 July 2020	
Protocol version 3.0	27 May 2020	
Protocol version 2.0	11 February 2020	
Protocol version 1.0	27 June 2019	

* Changes expected to require accommodation in analysis plan.

This SAP will govern the analysis of data from this study. Any deviations from the analysis plan will be documented as such in the study report.

II. Protocol Objectives and Analysis Endpoints

The overall objective is to evaluate the safety and tolerability of escalating doses of i.t. injections of SYNB1891 to determine the single-agent MTD as monotherapy and the RP2D in combination with atezolizumab.

Objective	Endpoints
Primary: 
Incidence of dose-limiting toxicities (DLTs): Percentage of patients who experience a DLT	
The number and percentage of patients who experience a DLT through the end of Cycle 1
Secondary: 
Nature, incidence, and severity of all adverse events (AEs) and serious adverse events (SAEs) according to the National Cancer Institute (NCI) Common Terminology Criteria for Adverse Events (CTCAE), version 5.0Objective response rate (ORR) as determined by the Response Evaluation Criteria in Solid Tumors, version 1.1 (RECIST 1.1) (Eisenhauer et al 2009), immune-related RECIST (iRECIST) (Seymour et al 2017), and/or the Lymphoma Response to Immunomodulatory Therapy Criteria (LYRIC) (Cheson et al 2016).	
The number and frequency of AEs and SAEs.The number and frequency of AEs and SAEs under each severity category.Objective response rate (complete response and partial response) per RECIST, iRECIST and LYRIC at any time on studyEvaluations of the SYNB1891-injected tumor(s), including tumor size, tumor response, etc.

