3. PK/Pharmacodynamic Population

The PK/PD population includes participants who received study drug and had at least one PK or PD assessment.

F. Data Display Characteristics

All analyses will be performed using SAS statistical analysis software. Descriptive statistics for continuous variables will include the number of patients, arithmetic mean, standard deviation (SD), median, minimum, and maximum. Geometric mean and geometric coefficient of variation (geoCV) may be used for PK/PD analyses. Summary statistics for categorical variables will contain count and percentage based on the number of patients in a cohort and the selected analysis population. Percentages will be presented to one decimal, except for one hundred percent, which will be presented as 100%.

Data displays produced for this study will include three types: summary tables, data listings and figures. Unless stated otherwise, data listings will be produced for all recorded data. Data listings will list the data recorded on the eCRF or obtained from external vendor for each patient. They will be ordered by arm, dose level, site, subject number, and time of assessment. When expedient, additional levels of ordering hierarchy may reflect subsets of assessments within an individual patient. Data listings will not display patient initials. Additional data listings may be produced for outcome measures that involve extensive procedures to derive the analyzed outcomes.

Summary tables will be produced as specified in following sections. Summary tables will display summary statistics calculated for each arm, dose cohorts and all patients combined, unless described otherwise in the following sections. For most summary tables, the arm and dose group will be presented in a column and the summary statistics of interest will be presented in rows.

Efficacy analysis will be summarized according to the planned dosing schedule. Safety analysis will be summarized according to the actual dosing schedule. For patients who were assigned a wrong study dose, they would be recoded in protocol deviation and dosing compliance; if the wrong dose occurred only once, the safety analysis will use the patients’ initial planned dose as summary cohorts. If more than one wrong dose occurred, the safety analysis will use patients’

actual dose as summary cohorts. If patients' doses were reduced, safety analysis will use the initial planned dose as summary cohorts.

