For lymphoma evaluated using LYRIC, the product of the perpendicular diameters (Longest Transverse Diameter \times Shortest Axis Perpendicular to Node) of the injected node will be listed per patient at each assessment visit. The change in the product of the perpendicular diameters will be summarized descriptively by comparing each follow up measurement to the baseline values. In addition, the percentage change of the product of the perpendicular diameters from baseline to the end of study for injected lesions will be displayed in waterfall plot by patient. A comparison of the percentage change between injected lesions and non-injected lesions (change in sum of the product of the perpendicular diameters) will also be presented in a waterfall plot for each patient.

VIII. Safety Analyses

Safety analyses will use data from the Safety population.

A. Treatment Exposure and Dosing Compliance

Exposure to SYNB1891 and atezolizumab will be summarized with descriptive statistics for the number of doses received, the number of cycles received, duration of dosing (weeks), total cumulative dose (cells/mL for SYNB1891, mg for atezolizumab). Duration of dosing is defined as the time from first dose of study drug in cycle 1 to the last dose of study drug in the last cycle a patient had.

The number of drug administrations with dose reduced, interrupted, and delayed will also be summarized descriptively by arm, cohort. In addition, the planned dosing date and the actual dosing date will be listed. Listings will be provided with the information from all the study drug administration eCRFs.

B. Dose Limiting Toxicities

Patients must have received at least one dose of the investigational product to be considered evaluable for the DLT evaluation and must have received at least 2 of the 3 planned SYNB1891 injections to contribute to dose-escalation decisions for a given cohort. DLTs will be determined for each patient through the end of Cycle 1. AEs and SAEs will be determined to be dose-limiting if they occur in this timeframe and meet the described criteria. AEs or SAEs experienced after the end of Cycle 1 will not be reported as DLTs but will be documented. Patients who experience a DLT (other than grade 5) will remain on the study to complete the safety evaluations and follow-up until resolution or stabilization of the DLT.

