19	Summary of Duration of Response by RECIST 1.1	Efficacy	

20	Summary of Duration of Response by LYRIC	Efficacy	
21	Dose Limiting Toxicity (DLT), Number (%) of Patients	Safety	X
22	Overall Summary of Treatment Emergent Adverse Events (TEAE), Number (%) of Patients	Safety	X
23	Incidence of Treatment Emergent Adverse Events by Primary MedDRA System Organ Class and Preferred Term, Number (%) of Patients	Safety	E1
24	Incidence of Treatment Emergent Adverse Events by System Organ Class and Preferred Term – Related to SYNB1891, Number (%) of Patients	Safety	E1
25	Incidence of Treatment Emergent Adverse Events by System Organ Class and Preferred Term – Related to Atezolizumab, Number (%) of Patients	Safety	
26	Incidence of Serious Treatment Emergent Adverse Events by System Organ Class and Preferred Term, Number (%) of Patients	Safety	E1
27	Incidence of Serious Treatment Emergent Adverse Events by System Organ Class and Preferred Term – Related to SYNB1891, Number (%) of Patients	Safety	E1
28	Incidence of Serious Treatment Emergent Adverse Events by System Organ Class and Preferred Term – Related to Atezolizumab, Number (%) of Patients	Safety	
29	Incidence of Grade 3 or Greater Treatment Emergent Adverse Events by System Organ Class and Preferred Term, Number (%) of Patients	Safety	E1
30	Incidence of Grade 3 or Greater Treatment Emergent Adverse Events by System Organ Class and Preferred Term – Related to SYNB1891, Number (%) of Patients	Safety	E1
31	Incidence of Grade 3 or Greater Treatment Emergent Adverse Events by System Organ Class and Preferred Term – Related to Atezolizumab, Number (%) of Patients	Safety	
32	Incidence of Treatment Emergent Adverse Events Leading to Any Study Drug Discontinuation by System Organ Class and Preferred Term, Number (%) of Patients	Safety	
33	Incidence of Treatment Emergent Adverse Events Leading to SYNB1891 Discontinuation by System Organ Class and Preferred Term, Number (%) of Patients	Safety	
34	Incidence of Treatment Emergent Adverse Events Leading to Atezolizumab Discontinuation by System Organ Class and Preferred Term, Number (%) of Patients	Safety	

35	Incidence of Treatment Emergent Adverse Events Resulting in SYNB1891 Dose Interruption by System Organ Class and Preferred Term, Number (%) of Patients	Safety	
36	Incidence of Treatment Emergent Adverse Events Resulting in Atezolizumab Dose Interruption by System Organ Class and Preferred Term, Number (%) of Patients	Safety	

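### The primary DLT percentage is reported on everyone dosed once, so it is too low at any dose with a DLT and a dosed patient the protocol calls non-evaluable

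*SAP*

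**What the plan says.** The primary endpoint in SAP section II is "The number and percentage of patients who experience a DLT through the end of Cycle 1".

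The protocol says who is evaluable. Section 4.2.3: "Patients must either experience a DLT during Cycle 1 or receive at least 2 of the 3 planned SYNB1891 injections to be considered evaluable". Under section 8.2.1, patients who leave before the second injection for a reason other than a DLT "will be considered ineligible for the safety assessment required for dose-escalation decisions and may be replaced". The mTPI decision table (Protocol Table 1, repeated in SAP Appendix 2) is indexed by the number of participants evaluable for DLT.

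The SAP splits that single rule in two. VIII.B says "Patients must have received at least one dose of the investigational product to be considered evaluable for the DLT evaluation", and adds that patients "must have received at least 2 of the 3 planned SYNB1891 injections to contribute to dose-escalation decisions for a given cohort". The reporting denominator follows from four places:

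- Section VIII opens with "Safety analyses will use data from the Safety population", which V.E defines by receipt of at least one dose.
- V.F says categorical summaries give "count and percentage based on the number of patients in a cohort and the selected analysis population".
- Appendix 5 lists Table 21, "Dose Limiting Toxicity (DLT), Number (%) of Patients", with Safety as its population, for both interim analyses.
- The overall safety summary in VIII.C also carries a DLT row.

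V.E defines Safety, Efficacy and PK/PD populations only, although Protocol 10.1 lets the SAP add others. Protocol 10.2 itself puts the DLT incidence tables under the safety variables, which use the safety population.

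**The concern.** A patient who receives one injection, has no DLT and leaves (for progression, say) is not evaluable under the protocol and may be replaced. In the SAP tables that patient stays in the denominator as someone without a DLT, and so does an evaluable replacement who has no DLT.

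The primary result could then differ from the counts on which the dose was escalated or held, and the difference always makes the dose look safer. Treating an incompletely observed patient as DLT-free also acts like imputing no DLT, which sits badly with SAP V.C, where imputation is ruled out for the primary objective.

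**Working it through.** **1. The plan's own figure.** Inputs from Protocol 4.2.3 and 10.6: initial cohorts of 3, one replacement allowed per cohort, up to 7 cohorts in Arm 1 and 5 in Arm 2, and up to 20 expansion patients.

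7 × (3 + 1) + 5 × (3 + 1) + 20 = 28 + 20 + 20 = 68, against a stated total of approximately 70.

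The 28 and 20 also match the study design figure text. So the plan budgets for replaced patients, although this is an allowance and not a forecast.

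**2. Direction.** Let x be the number of patients with a Cycle 1 DLT at a dose, n the number evaluable under Protocol 4.2.3, and k the number dosed but not evaluable.

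- Every patient with a Cycle 1 DLT is evaluable under 4.2.3 and, having been dosed, is in the Safety population. The numerator x is the same in both sets.
- Evaluable rate = x/n. Rate as tabulated = x/(n + k).
- Difference = xk / [n(n + k)]. This is zero when x = 0 or k = 0, and otherwise always a reduction.

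**3. Size with one such patient (k = 1).**

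| Evaluable set | Safety population | Loss (points) | Table 1 decision on evaluable set |
|---|---|---|---|
| 1/3 = 33.3% | 1/4 = 25.0% | 8.3 | stay |
| 2/6 = 33.3% | 2/7 = 28.6% | 4.8 | stay |
| 3/10 = 30.0% | 3/11 = 27.3% | 2.7 | stay |
| 4/14 = 28.6% | 4/15 = 26.7% | 1.9 | stay |

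With k = 2, which is an assumption, the last three rows become 2/8, 3/12 and 4/16, each 25.0%. The losses are then 8.3, 5.0 and 3.6 points.

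**4. Which rows can be a final result.** Table 1 says stay at 1 DLT in 3, so that dose normally enrolls more patients. The first row therefore describes a passing state, such as a dose that happens to stand there when an interim table is cut. A dose that Table 1 moves away from after 3 evaluable patients has 0, 2 or 3 DLTs. Zero gives 0% in both sets. The other two give 2/3 = 66.7% against 2/4 = 50.0%, and 3/3 = 100% against 3/4 = 75.0%, well above the 30% target either way. The relevant rows for a selected dose are the expanded ones.

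**The case against.** The best defense is that the SAP follows the protocol's own analysis section. Protocol 10.2 runs safety analyses on the safety population and lists DLT incidence tables there. The primary endpoint in 3.1 is a percentage of patients, with no evaluability restriction. Section 8.2.1 limits ineligibility to the assessment for dose-escalation decisions. This stands in part: the gap belongs to both documents, not to the SAP alone. It does not explain why SAP VIII.B gives *evaluable* a meaning that contradicts Protocol 4.2.3, or why no estimate on the protocol's evaluable set is planned.

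It can also be said that the evaluable rate is recoverable, because counts, DLTs and every administration are tabulated or listed, and that final shells sit in a separate document. That is true, but a reader should not have to rebuild the primary endpoint from listings.

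A reader might infer stronger things that the documents do not support:

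- *That the rate is lowered at every dose.* It changes only where x and k are both at least 1. Patients replaced before any dose are outside the Safety population and add nothing, and replacement is optional.
- *That a dose selected near 30% would be reported at 22.5%.* That figure is 0.30 × 3/4 and needs a dose that stays at 3 evaluable patients, which Table 1 does not normally allow near the target. At 6 + 1 patients a true 30% is reported on average as 0.30 × 6/7 = 25.7%, and at 14 + 1 as 0.30 × 14/15 = 28.0%.
- *That escalation or the choice of MTD is distorted.* The mTPI table uses evaluable participants, SAP VIII.B keeps the 2-of-3 rule for escalation, and nothing says that the by-dose rate estimates in Protocol 4.2.3 use the Safety denominator.

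**Conclusion.** The point holds as a reporting error in the primary endpoint. Where a dose has at least one DLT and at least one dosed non-evaluable patient, the planned percentage is below the rate on the protocol's evaluable set and does not match the mTPI counts. With one such patient the loss is about 2 to 5 points for a dose expanded to between 6 and 14 evaluable patients and standing near 30%. It is 8.3 points only while a dose stands at 1 DLT in 3.

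The size depends on how many patients are dosed and then leave before a second injection without a DLT; the documents give an allowance for replacements but no expected number. If there are none, the two rates agree. The error is modest, but it runs in one direction, affects the primary endpoint and is simple to remove.

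**What to change.** - Define a DLT-evaluable population in SAP V.E with the Protocol 4.2.3 wording: a Cycle 1 DLT, or at least 2 of the 3 planned injections.
- Use it as the denominator for Table 21, for the DLT row of the overall safety summary, and for the by-dose DLT-rate estimates. Changing Table 21 alone would leave the two displays in conflict.
- Show the Safety-population percentage and the number of dosed but non-evaluable patients per dose as supportive rows.
- Reconcile the evaluability sentence in SAP VIII.B with Protocol 4.2.3 and 10.2. That sentence also omits the protocol's Cycle 1 DLT alternative when it states who contributes to escalation, so the two passages need to be brought into line there as well.

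The cost is SAP wording and one population flag, with no new data. Reported DLT rates may be slightly higher.
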